### **7.1.2.7 Tissue Collection and Correlative Studies Blood Sampling**

Subjects who enroll on this study will have the option to provide tissue and blood samples for correlative studies, as described above in Section 4.2.3.2. Subjects may enroll on this study and opt out of these additional tests.

Bone marrow samples available from screening, post-cycle 1, post-cycle 2, post-cycle 4, and end-of-treatment will undergo DNA extraction in order to perform NGS-based MRD assessments. As these assays require knowledge of the leukemia-specific sequence from a sample with relatively high disease burden (e.g., initial diagnosis or morphologic relapse), archived tissue will be requested in order to identify this. In the event that this baseline sample cannot be obtained, then collection of samples for these exploratory MRD assessments may be deferred at the discretion of the PI. Lastly, DNA will be extracted from bone marrow obtained post-cycle 4 (for those patients still enrolled at that time) to investigate for clonal changes in the immune microenvironment.

As close as feasible to the timing of these marrow examinations at screening, post-cycle 2, post-cycle 4, and end-of-treatment, peripheral blood will also be collected for additional correlative studies. Flow cytometry will be performed in the UW Hematopathology Laboratory to assess for changes in circulating T-cell subsets (e.g., cytotoxic T cells, regulatory T cells) and other markers of cellular immunologic response. DNA will also be extracted to investigate for clonal changes in the immune repertoire. Lastly, cytokine and inflammatory marker measurements will occur in the IML at FHCRC and can include (but not necessarily limited to) PD-L1, interleukin (IL)-2, IL-21, and tumor necrosis factor alpha.

### **7.1.3 Laboratory Procedures/Assessments**

Details regarding specific laboratory procedures/assessments to be performed in this trial are provided below.

Laboratory tests for hematology, chemistry, urinalysis, and others are specified in Table 5.

9458- Protocol Version Date 28 Feb 2019

Table 5: Laboratory Tests

Hematology	Chemistry	Urinalysis	Other
Hematocrit	Albumin	Blood	Serum $\beta$ -human chorionic gonadotropin†
Hemoglobin	Alkaline phosphatase	Glucose	( $\beta$ -hCG)†
Platelet count	Alanine aminotransferase (ALT)	Protein	PT (INR)
WBC (total and differential)	Aspartate aminotransferase (AST)	Specific gravity	aPTT
Red Blood Cell Count	Lactate dehydrogenase (LDH)	Microscopic exam ( If abnormal, results are noted )	Total triiodothyronine (T3)
Absolute Neutrophil Count	Carbon Dioxide	Urine pregnancy test †	Free thyroxine (T4)
Absolute Lymphocyte Count	( CO2 or biocarbonate )		Thyroid stimulating hormone (TSH)
	Uric Acid		
	Calcium		
	Chloride		Blood for correlative studies
	Glucose		
	Phosphorus		
	Potassium		
	Sodium		
	Magnesium		
	Total Bilirubin		
	Direct Bilirubin ( If total bilirubin is elevated above the upper limit of normal )		
	Total protein		
	Blood Urea Nitrogen		

† Perform on women of childbearing potential only. If urine pregnancy results cannot be confirmed as negative, a serum pregnancy test will be required.

9458- Protocol Version Date 28 Feb 2019

Laboratory tests for screening or entry into the Second Course Phase should be performed within 10 days prior to the first dose of treatment. After Cycle 1, pre-dose laboratory procedures can be conducted up to 3 days prior to dosing. Results must be reviewed by the investigator or qualified designee and found to be acceptable prior to each dose of trial treatment.

#### **7.1.3.1 Pharmacokinetic/Pharmacodynamic Evaluations**

There will not be any formal pharmacokinetic/pharmacodynamic evaluations as part of this study, apart from those described in Section 7.1.2.7.

#### **7.1.4 Other Procedures**

##### **7.1.4.1 Withdrawal/Discontinuation**

When a subject discontinues/withdraws prior to trial completion, all applicable activities scheduled for the final trial visit should be performed at the time of discontinuation. Any adverse events which are present at the time of discontinuation/withdrawal should be followed in accordance with the safety requirements outlined in Section 7.2 - Assessing and Recording Adverse Events. Subjects who a) attain a CR or b) complete 24 months of treatment with pembrolizumab may discontinue treatment with the option of restarting treatment if they meet the criteria specified in Section 7.1.5.5. After discontinuing treatment following assessment of CR, these subjects should proceed to the Follow-Up Period of the study (described in Section 7.1.5.4).

##### **7.1.4.2 Blinding/Unblinding**

No blinding will be performed on this trial.

#### **7.1.5 Visit Requirements**

Visit requirements are outlined in Section 6.0 - Trial Flow Chart. Specific procedure-related details are provided above in Section 7.1 - Trial Procedures.

##### **7.1.5.1 Screening**

###### **7.1.5.1.1 Screening Period**

Screening evaluations as listed in Section 6.0 - Trial Flow Chart may occur within 28 days of initiation of treatment, with the following two exceptions: laboratory assessments (as mentioned above) should be obtained within 10 days, and urine/serum pregnancy test must be performed within 3 days of the first dose of pembrolizumab.

##### **7.1.5.2 Treatment Period**

Treatment will occur every 3 weeks ( $21 \pm 3$  days). Clinical and laboratory procedures/assessments (as delineated in Section 6.0) should occur within 3 days of administration of pembrolizumab. In the event that these assessments performed for screening

9458- Protocol Version Date 28 Feb 2019

purposes occur within 3 days of the start of Cycle 1, they do not need to be repeated for Cycle 1. Response assessments by bone marrow examination will be performed as described in Section 7.1.2.6.

### **7.1.5.3 Post-Treatment Visits**

#### **7.1.5.3.1 Safety Follow-Up**

Subjects with an AE of Grade > 1 will be followed until the resolution of the AE to Grade 0-1 or until the beginning of a new anti-neoplastic therapy, whichever occurs first. SAEs that occur within 90 days of the end of treatment or before initiation of a new anti-cancer treatment (whichever comes first) should also be followed and recorded.

#### **7.1.5.3.2 Follow-up Visits**

Subjects who discontinue trial treatment for a reason other than disease progression will move into the Follow-Up Phase and should be assessed approximately every 3 months for up to 2 years. These assessments may be performed by local or referring medical providers, provided appropriate medical records can be made available to research staff. Every effort should be made to collect information regarding disease status until the start of new anti-neoplastic therapy, disease progression, death, end of the study or if the subject begins retreatment with pembrolizumab as detailed in Section 7.1.5.5. Information regarding post-study anti-neoplastic treatment will be collected if new treatment is initiated. If this anti-neoplastic treatment includes allogeneic HCT, occurrence of graft rejection and/or grade 3 or higher acute GVHD according to section 12.4 will be noted.

Subjects who are eligible to receive retreatment with pembrolizumab according to the criteria in Section 7.1.5.5 will move from the follow-up phase to the Second Course Phase when they experience disease progression. Details are provided in Section 6.1 – Trial Flow Chart (i.e., Second Course Phase will be identical to initial treatment).

#### **7.1.5.3.3 Survival Follow-up**

Once a subject experiences confirmed disease progression or starts a new anti-cancer therapy, the subject moves into the survival follow-up phase and should be contacted (via medical record review and/or telephone) approximately every 3 months to assess for survival status until death, withdrawal of consent, or the end of the study, whichever occurs first.

### **7.1.5.4 Second Course Phase (Retreatment Period)**

Subjects who stop pembrolizumab in a complete MRD response may be eligible for up to one year of additional pembrolizumab therapy if they experience MRD reappearance after stopping study treatment. This retreatment is termed the Second Course Phase of this study and is only available if the study remains open and the subject meets the following conditions:

- Stopped initial treatment with pembrolizumab after attaining an investigator-determined confirmed complete MRD response according to consensus criteria, and

9458- Protocol Version Date 28 Feb 2019

- Was treated for at least 24 weeks with pembrolizumab before discontinuing therapy
- Received at least two treatments with pembrolizumab beyond the date when the initial complete MRD response was declared
- Experienced an investigator-determined confirmed MRD reappearance after stopping their initial treatment with pembrolizumab
- Did not receive any anti-cancer treatment since the last dose of pembrolizumab
- Has a performance status of 0 or 1 on the ECOG Performance Scale
- Demonstrates adequate organ function as detailed in Section 5.1.2
- Female subject of childbearing potential should have a negative serum or urine pregnancy test within 3 days prior to receiving retreatment with study medication.
- Female subject of childbearing potential should be willing to use 2 methods of birth control or be surgically sterile, or abstain from heterosexual activity for the course of the study through 120 days after the last dose of study medication (Reference Section 5.7.2). Subjects of child bearing potential are those who have not been surgically sterilized or have been free from menses for > 1 year.
- Male subject should agree to use a condom starting with the first dose of study therapy through 120 days after the last dose of study therapy.
- Does not have a history or current evidence of any condition, therapy, or laboratory abnormality that might interfere with the subject's participation for the full duration of the trial or is not in the best interest of the subject to participate, in the opinion of the treating investigator.

Subjects who restart treatment will be retreated at the same dose and dose interval as when they last received pembrolizumab. Treatment will be administered for up to one additional year.

Visit requirements are outlined in Section 6.1 – Trial Flow Chart.

## **7.2 Assessing and Recording Adverse Events**

An adverse event is defined as any untoward medical occurrence in a patient or clinical investigation subject administered a pharmaceutical product and which does not necessarily have to have a causal relationship with this treatment. An adverse event can therefore be any unfavorable and unintended sign (including an abnormal laboratory finding, for example), symptom, or disease temporally associated with the use of a medicinal product or protocol-specified procedure, whether or not considered related to the medicinal product or protocol-specified procedure. Any worsening (i.e., any clinically significant adverse change in

9458- Protocol Version Date 28 Feb 2019

frequency and/or intensity) of a preexisting condition that is temporally associated with the use of Merck's product is also an adverse event.

Changes resulting from normal growth and development that do not vary significantly in frequency or severity from expected levels are not to be considered adverse events. Examples of this may include, but are not limited to, menopause occurring at a physiologically appropriate time.

Merck product includes any pharmaceutical product, biological product, device, diagnostic agent or protocol-specified procedure, whether investigational (including placebo or active comparator medication) or marketed, manufactured by, licensed by, provided by or distributed by Merck for human use.

Adverse events may occur during the course of the use of Merck product in clinical trials or within the follow-up period specified by the protocol, or prescribed in clinical practice, from overdose (whether accidental or intentional), from abuse and from withdrawal.

Adverse events may also occur in screened subjects during any pre-allocation baseline period as a result of a protocol-specified intervention, including washout or discontinuation of usual therapy, diet, placebo treatment or a procedure.

Relapse/progression of ALL is not considered an adverse event unless it is considered to be drug related by the investigator.

All ECIs (as defined in Section 7.2.3.2) and other grade 3 or higher adverse events will be recorded from the time the consent form is signed through 30 days following cessation of treatment and at each examination on the Adverse Event case report forms/worksheets. The reporting timeframe for adverse events meeting any serious criteria is described in section 7.2.3.1.

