#### 3.2 Secondary Objectives & Hypotheses

- (1) **Objective:** To describe the toxicity profile of pembrolizumab in patients with previously-treated ALL.

**Hypothesis:** Pembrolizumab will be safe and well-tolerated in this patient population.

- (2) **Objective:** To gain a preliminary assessment of how MRD response translates into relapse-free and overall survival.

**Hypothesis:** Patients that experience a complete MRD response will have longer morphologic relapse-free and overall survival than those who do not.

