## **7.1.2 Clinical Procedures/Assessments**

### **7.1.2.1 Adverse Event (AE) Monitoring**

The investigator or qualified designee will assess each subject to evaluate for potential new or worsening AEs as specified in the Trial Flow Chart and more frequently if clinically indicated. Adverse experiences will be graded and recorded throughout the study and during the follow-up period according to the most current available version of the NCI CTCAE (see Section 12.2). Toxicities will be characterized in terms regarding seriousness, causality, toxicity grading, and action taken with regard to trial treatment.

Please refer to section 7.2 for detailed information regarding the assessment and recording of AEs.

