#### **7.2.4 Evaluating Adverse Events**

An investigator who is a qualified physician will evaluate all adverse events according to the most current available version of NCI Common Terminology for Adverse Events (CTCAE). Any adverse event which changes CTCAE grade over the course of a given episode will have each change of grade recorded on the adverse event case report forms/worksheets.

All adverse events regardless of CTCAE grade must also be evaluated for seriousness.

9458- Protocol Version Date 28 Feb 2019

Table 6: Evaluating Adverse Events

An investigator, who is a qualified physician, will evaluate all adverse events as to:

CTCAE Grading	Grade 1	Mild; asymptomatic or mild symptoms; clinical or diagnostic observations only; intervention not indicated.
	Grade 2	Moderate; minimal, local or noninvasive intervention indicated; limiting age-appropriate instrumental ADL.
	Grade 3	Severe or medically significant but not immediately life-threatening; hospitalization or prolongation of hospitalization indicated; disabling; limiting self-care ADL.
	Grade 4	Life threatening consequences; urgent intervention indicated.
	Grade 5	Death related to AE
Seriousness	A serious adverse event is any adverse event occurring at any dose or during any use of Merck product that:	
	†Results in death; or	
	†Is life threatening; or places the subject, in the view of the investigator, at immediate risk of death from the event as it occurred (Note: This does not include an adverse event that, had it occurred in a more severe form, might have caused death.); or	
	†Results in a persistent or significant disability/incapacity (substantial disruption of one's ability to conduct normal life functions); or	
	†Results in or prolongs an existing inpatient hospitalization (hospitalization is defined as an inpatient admission, regardless of length of stay, even if the hospitalization is a precautionary measure for continued observation. (Note: Hospitalization [including hospitalization for an elective procedure] for a preexisting condition which has not worsened does not constitute a serious adverse event.); or	
	†Is a congenital anomaly/birth defect (in offspring of subject taking the product regardless of time to diagnosis); or	
	Is a new cancer; (that is not a condition of the study) or	

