	Is an overdose (whether accidental or intentional). Any adverse event associated with an overdose is considered a serious adverse event. An overdose that is not associated with an adverse event is considered a non-serious event of clinical interest and must be reported within 24 hours.	
	Other important medical events that may not result in death, not be life threatening, or not require hospitalization may be considered a serious adverse event when, based upon appropriate medical judgment, the event may jeopardize the subject and may require medical or surgical intervention to prevent one of the outcomes listed previously (designated above by a †).	
Duration	Record the start and stop dates of the adverse event. If less than 1 day, indicate the appropriate length of time and units	
Action taken	Did the adverse event cause the Merck product to be discontinued?	
Relationship to test drug	Did the Merck product cause the adverse event? The determination of the likelihood that the Merck product caused the adverse event will be provided by an investigator who is a qualified physician. The investigator's signed/dated initials on the source document or worksheet that supports the causality noted on the AE form, ensures that a medically qualified assessment of causality was done. This initialed document must be retained for the required regulatory time frame. The criteria below are intended as reference guidelines to assist the investigator in assessing the likelihood of a relationship between the test drug and the adverse event based upon the available information.	
	The following components are to be used to assess the relationship between the Merck product and the AE; the greater the correlation with the components and their respective elements (in number and/or intensity), the more likely the Merck product caused the adverse event (AE):	
	Exposure	Is there evidence that the subject was actually exposed to the Merck product such as: reliable history, acceptable compliance assessment (pill count, diary, etc.), expected pharmacologic effect, or measurement of drug/metabolite in bodily specimen?
	Time Course	Did the AE follow in a reasonable temporal sequence from administration of the Merck product? Is the time of onset of the AE compatible with a drug-induced effect (applies to trials with investigational medicinal product)?

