	Likely Cause	Is the AE not reasonably explained by another etiology such as underlying disease, other drug(s)/vaccine(s), or other host or environmental factors

9458- Protocol Version Date 28 Feb 2019

Relationship to Merck product (continued)	The following components are to be used to assess the relationship between the test drug and the AE: (continued)	
	Dechallenge	
Was the Merck product discontinued or dose/exposure/frequency reduced?                      If yes, did the AE resolve or improve?                      If yes, this is a positive dechallenge. If no, this is a negative dechallenge.                      (Note: This criterion is not applicable if: (1) the AE resulted in death or permanent disability; (2) the AE resolved/improved despite continuation of the Merck product; or (3) the trial is a single-dose drug trial); or (4) Merck product(s) is/are only used one time.)

	Rechallenge	
Was the subject re-exposed to the Merck product in this study?                      If yes, did the AE recur or worsen?                      If yes, this is a positive rechallenge. If no, this is a negative rechallenge.                      (Note: This criterion is not applicable if: (1) the initial AE resulted in death or permanent disability, or (2) the trial is a single-dose drug trial); or (3) Merck product(s) is/are used only one time).                      NOTE: IF A RECHALLENGE IS PLANNED FOR AN ADVERSE EVENT WHICH WAS SERIOUS AND WHICH MAY HAVE BEEN CAUSED BY THE MERCK PRODUCT, OR IF REEXPOSURE TO THE MERCK PRODUCT POSES ADDITIONAL POTENTIAL SIGNIFICANT RISK TO THE SUBJECT, THEN THE RECHALLENGE MUST BE APPROVED IN ADVANCE BY THE U.S. CLINICAL MONITOR AS PER DOSE MODIFICATION GUIDELINES IN THE PROTOCOL.

	Consistency with Trial Treatment Profile	
Is the clinical/pathological presentation of the AE consistent with previous knowledge regarding the Merck product or drug class pharmacology or toxicology?

The assessment of relationship will be reported on the case report forms /worksheets by an investigator who is a qualified physician according to his/her best clinical judgment, including consideration of the above elements.
		
Record one of the following	Use the following scale of criteria as guidance (not all criteria must be present to be indicative of a Merck product relationship).	

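### The protocol does not say which recording scope governs the adverse event form, so entry of non-serious grade 1–2 events that hold or stop pembrolizumab is not assured

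*Combined protocol and SAP*

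**What the plan says.** Section 7.2 is the passage that fixes both scope and window for entries on the AE case report forms. ECIs "and other grade 3 or higher adverse events will be recorded from the time the consent form is signed through 30 days following cessation" (treatment's end). Serious events are sent to Section 7.2.3.1. Section 7.2.3.2 lists two ECIs: an overdose without clinical or laboratory consequences, and a combined pattern of raised AST or ALT, raised bilirubin and alkaline phosphatase below twice the upper limit.

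Other passages have no grade floor:

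- Section 7.1.2.1: "Adverse experiences will be graded and recorded throughout the study and during the follow-up period". It adds that toxicities are described by seriousness, cause, grade and what was done about trial treatment. It then sends the reader back to 7.2: "Please refer to section 7.2 for detailed information regarding the assessment and recording of AEs".
- Section 7.2.4: "Any adverse event which changes CTCAE grade over the course of a given episode will have each change of grade recorded", and the place named for this is the AE form.
- Table 6: "An investigator, who is a qualified physician, will evaluate all adverse events as to" grade, seriousness, duration, action taken and relationship. The action item asks "Did the adverse event cause the Merck product to be discontinued". On causality, "The assessment of relationship will be reported on the case report forms /worksheets by an investigator who is a qualified physician".

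The term ECI is also used more widely than the list. Section 5.5.2 permits systemic steroids for ECIs of suspected immune origin. Section 5.6.1 tells the investigator to follow ECI reporting for events in the immune guidance that are judged unrelated to the drug.

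The data feed the first secondary objective in Section 3.2: "To describe the toxicity profile of pembrolizumab in patients with previously-treated ALL". Section 9.2 says that secondary endpoints, toxicity included, are reported mainly descriptively.

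**The concern.** A stated threshold matters only if events below it may be treated differently. Section 7.2 names grade 3. Section 7.1.2.1 has no floor but defers to 7.2 for detail, which is where the floor stands. Staff completing the form could reasonably adopt either scope.

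The choice matters because the protocol itself treats many events below grade 3 as reason to withhold or end pembrolizumab. The hypothesis attached to this objective is that the drug will be safe and tolerable, and toxicity that interrupts or ends treatment bears directly on that. A descriptive profile contains only what was entered. Under the 7.2 floor, a non-serious grade 2 event that interrupted or ended treatment could have no AE entry with grade and causality.

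**Working it through.** No power or error-rate calculation applies. The check compares the recording rules with the protocol's own hold and stop triggers.

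**1. Triggers below grade 3.** Table 3 has 10 immune-related rows.

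| Table 3 row | Withheld at grade 2 or lower? |
|---|---|
| Pneumonitis | Yes, grade 2 |
| Diarrhea/colitis | Yes, grade 2 |
| AST/ALT or bilirubin | Yes, grade 2 |
| Type 1 diabetes/hyperglycemia | Not counted: new-onset diabetes has no grade stated; hyperglycemia is grade 3 or 4 |
| Hypophysitis | Yes, grade 2 |
| Hyperthyroidism | No, continued at grade 2 |
| Hypothyroidism | No, continued |
| Nephritis/renal dysfunction | Yes, grade 2 |
| Myocarditis | Yes, grade 1 or 2 |
| All other immune-related | Yes, grade 2 if intolerable or persistent |

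Rows that withhold at grade 2 or lower: 10 − 3 = 7.

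**2. Permanent stops at grade 2.** Recurrent grade 2 pneumonitis (Table 3) and a grade 2 infusion reaction despite premedication (Table 4): 1 + 1 = 2.

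**3. Which of these the 7.2 rule reaches.** A non-serious event below grade 3 qualifies only as an ECI. On the list in 7.2.3.2, that is possible for 1 of the 7 rows (hepatic), and only if the whole combined pattern is met. The other 7 − 1 = 6 rows have no route through that list. The wider use of ECI in 5.5.2 and 5.6.1 might supply one, but those sections list no events to be recorded.

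**4. What the grade-change rule in 7.2.4 would add.** Table 3's general instructions allow a withheld drug to be resumed once the event has fallen to grade 1 or 0. A grade 2 event followed by resumption has therefore changed grade and would be entered under 7.2.4. Recurrent grade 2 pneumonitis implies a preceding episode that improved. Section 5.6.1 says infusion reactions usually clear within 24 hours. If resolution counts as a change of grade, both stopping cases are probably entered.

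**5. What remains.** Events whose grade does not change: for example, myocarditis that stays at grade 1, or a persistent grade 2 event after which treatment is not resumed.

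**6. What other records hold.** Concomitant medications (5.5.1), protocol therapy (Section 11.5 and the text printed after it) and follow-up of AEs above grade 1 (7.1.5.3.1) would leave traces. None of them requires an AE form entry with grade and causality. The action question in Table 6 asks about discontinuation. Holds come in only through the general wording of 7.1.2.1.

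**The case against.** The strongest reply is that the rules do not conflict. Section 7.2 says what will be recorded; it does not say that nothing else will be. Staff can obey 7.2, 7.1.2.1, 7.2.4 and Table 6 together by entering everything that any of them requires. Section 7.1.2.1 already asks, at every grade, what was done with trial treatment, which covers holds as well as stops. This stands. A reader might infer that 7.2 bars lower-grade entries or flatly contradicts the other sections, and the documents do not support that.

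A reader might also infer that the two grade 2 stopping rules produce discontinuations with no AE entry. That is too strong as well, since 7.2.4 would probably capture both. Nor does any sentence declare the two-item ECI list complete, and 5.5.2 and 5.6.1 suggest a wider class, so the count of 6 rows without an ECI route holds only for the list as printed.

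The difference in ECI windows might be read as a further loss: 30 days for recording in 7.2 against up to 90 days for reporting in 7.2.3.2, a gap of 90 − 30 = 60 days, or none if new anticancer therapy starts. But recording on the form and reporting to the manufacturer are separate duties, and a reported ECI is still captured. This is marginal.

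Finally, this is a single-institution trial of 21 patients, so sites cannot diverge. That limits the harm but does not tell the one site which scope to use. The reply leaves standing that no passage says which scope governs the form.

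**Conclusion.** The recording scope for the AE form is unreconciled. If the 7.2 floor is applied, entry is not assured for non-serious events of grade 2 or lower that hold pembrolizumab (7 of 10 rows) or stop it (2 rules). If 7.2.4 is followed literally, most of these are entered and a small residue of unchanging-grade events remains.

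These figures count protocol rules, not patients. With no event rate in the documents, the number of the 21 patients affected cannot be given. The conclusion assumes that staff could read the grade 3 threshold as the working limit. Serious events fall under their own rule and are not affected. Neither are the primary endpoint and the early-relapse stopping rule. One descriptive secondary endpoint is touched, so the severity is minor.

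**What to change.** Reconcile 7.2 with 7.1.2.1, 7.2.4 and Table 6:

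- State in 7.2 that, besides ECIs and grade 3 or higher events, any AE that leads to withholding or discontinuation of pembrolizumab is entered on the AE form whatever its grade, with the action taken recorded as hold or stop.
- State whether the grade floor applies to all other grade 1–2 events.
- Bring the use of ECI in 5.5.2 and 5.6.1 into line with the list in 7.2.3.2.

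The cost is a few sentences and a few more form entries among 21 patients. The flow chart already reviews AEs at every cycle. The reported toxicity profile may look somewhat less favorable. No dose or management rule changes.
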